## I. BACKGROUND AND SIGNIFICANCE

Diabetes mellitus (DM) and prediabetic states are enormous public health burdens in the US and worldwide. Recent statistics approximate that 25.8 million children and adults in the US—8.3% of the population have DM. Alarming, an additional 79 million people are estimated to have prediabetes, and this is likely to increase with the rising prevalence of obesity in the population. Meta-analyses of large prospective studies suggest that, after accounting for other risk factors, DM more than doubles the risk of coronary artery disease (CAD) and ischemic stroke, and that this DM-related risk is higher in women than in men. In contrast with the strong associations observed between type 2 DM and related cardiometabolic disorders and cardiovascular outcomes, a recent meta-analysis of 102 prospective studies found a very modest association of fasting glucose level with CAD and stroke risk. Moreover, large intervention trials have shown no beneficial effect of intensive glucose control on primary cardiovascular endpoints. While glucose level itself may play some role in modulating cardiovascular risk, the mechanisms mediating increased risk of cardiovascular mortality and morbidity in diabetics are not well understood. Although a greater extent of CAD, as well as abnormalities in cardiac structure and function have been implicated in diabetics, these pathophysiologic features provide only a partial explanation to the excess risk of MI, heart failure and death among diabetics and patients with metabolic syndrome. Indeed, the extent of luminal angiographic CAD with or without left ventricular (LV) dysfunction does not fully account for the excess clinical risk among subjects with or without DM. In our work, the presence of impaired coronary flow reserve (CFR) in patients without overt obstructive CAD identifies patients at increased risk of adverse cardiac events, and diabetic patients without known CAD with impaired CFR show a risk of cardiac death comparable to, and possibly higher than, that for nondiabetic patients with known CAD. This suggests that diffuse atherosclerosis and coronary microvascular dysfunction play a more important role than previously appreciated in the pathophysiologic abnormalities leading to increased risk.

Interestingly, this excess risk may be linked to an enhanced pro-inflammatory state, consistently demonstrated in patients with type 2 DM and metabolic syndrome, and following acute MI. Exactly how the enhanced pro-inflammatory response in DM and metabolic syndrome is associated with increased risk of adverse outcomes is not well understood. There is ample laboratory evidence that inflammation plays a major role in all stages of atherothrombosis including the early functional abnormalities in vascular endothelial and smooth muscle cell function. There is also growing *in vivo* human evidence that increased systemic inflammation is associated with coronary vascular dysfunction. Moreover, there is preliminary evidence that anti-inflammatory therapies may lead to improved coronary vasoreactivity.

To date, however, no trial has yet proven that directly reducing inflammation lowers cardiovascular event rates, and the Cardiovascular Inflammation Reduction Trial (CIRT) has been launched to address this issue. A possible mechanism for doing so may involve systemic improvement in global coronary vascular function. As such, CIRT provides a *unique* opportunity to assess whether CFR might provide a simple noninvasive method to predict which patients best respond to a systemic anti-inflammatory intervention. *By testing the fundamental concept of whether reducing systemic inflammation can lead to improved myocardial blood flow, tissue perfusion and LV function, CIRT-CFR, our proposed randomized placebo-controlled ancillary clinical trial, would provide important mechanistic insights of the capabilities of an anti-inflammatory therapy to improve key clinical determinants of clinical risk.* Equally important for

continued research development programs and eventual future clinical decision-making is the validation of a physiologic imaging biomarker that could also be used to evaluate safety and efficacy of novel therapeutic agents during drug development programs, and/or identify patients at particularly high risk in need of aggressive therapeutic intervention.

The Cardiovascular Inflammation Reduction Trial (CIRT) is an NHLBI funded multicenter clinical trial (U01 HL 101422) that will randomly allocate 7,000 patients with stable CAD and either type 2 DM or metabolic syndrome to low-dose methotrexate (LDM; target dose 15 to 20 mg per week) plus usual care, or placebo plus usual care over a follow-up period of 2 to 4 years (average 3 years). CIRT is an event-driven trial such that in the absence of extreme effects, the trial will conclude after accrual of at least 530 primary endpoints, estimated to provide 90% power to detect a 25% relative risk reduction. The CIRT primary endpoint is a composite of nonfatal myocardial infarction (MI), stroke, and cardiovascular death. Secondary endpoints include total mortality, coronary revascularization, unstable angina requiring unplanned revascularization, and hospitalization for heart failure, with additional pre-specified endpoints such as incident venous thrombosis, atrial fibrillation, peripheral artery disease, and severe aortic stenosis. In addition, effects on measures of quality of life will be assessed using the standardized SF-36 Health Survey. Participants will be recruited from roughly 400 clinical sites in the United States and Canada.

In addition to LDM or matching placebo, all study participants (including those on placebo) will receive folic acid 1.0 mg 6 days per week, a therapy known to reduce side effects that can be associated with LDM. To further ensure safety and improve long-term compliance, the trial design incorporates a 5- to 6-week open-label, active-therapy run-in (maximum 8 weeks) for all potentially eligible participants so that those unable to initially tolerate LDM are excluded prior to randomization. Additional details of the CIRT parent trial are included in the appended CIRT IRB application, approved on 6/13/2012 (Appendix).

The proposed ancillary imaging trial, CIRT-CFR, is a randomized placebo-controlled clinical trial that will test directly whether reducing systemic inflammation in stable CAD patients improves myocardial perfusion reserve, as measured by CFR, a novel quantitative imaging marker of clinical risk. Coronary flow reserve (CFR) refers to the ratio of global myocardial blood flow quantified at stress over that at rest. CFR provides a robust measure of the *integrated* hemodynamic effects of epicardial CAD, diffuse atherosclerosis, vessel remodeling, and microvascular dysfunction on myocardial perfusion. CFR quantified using vasodilator PET can identify patients at high risk for serious cardiac adverse events, including cardiac death, even in the absence of overt obstructive disease (i.e. independently of perfusion score), and these associations are especially evident among high, but heterogeneous risk cohorts including patients with DM. The demonstration of improved CFR and myocardial perfusion after low-dose methotrexate would provide further validation of this imaging biomarker as a potential indicator of the complex sequelae of active inflammation in the heart. Doing so may provide a direct, quantifiable target that could be useful in drug discovery programs, and perhaps for initiation and monitoring of therapeutic efficacy.

Specifically, this trial aims to investigate a mechanism by which LDM may modulate cardiovascular outcomes in a high-risk population enriched for chronic, low-level inflammation. Increasing data suggest that LDM, a generic therapy that is widely used among patients with rheumatoid arthritis and psoriasis, mediates its beneficial effects not by direct inhibition of cellular proliferation, but by promoting release of the robust anti-inflammatory autacoid, *adenosine*, at sites of inflammation. Increased extracellular concentrations of adenosine modulate recruitment

and function of leukocytes, including neutrophils, macrophages and regulatory T lymphocytes, leading to local and systemic reduction of inflammatory cytokines such as IL-12, IL-6 and TNF, with far-reaching effects that include facilitated cholesterol efflux and reverse cholesterol transport from arterial wall foam cells. Moreover, adenosine mediates these effects while acting as a potent vasodilator. As such, treatment with LDM is poised to affect coronary vasoreactivity in diabetics and prediabetics in complex ways that are ripe for study using PET measures of CFR.

Another fundamental physiologic principle of our study is that, by decreasing inflammation and enhancing myocardial tissue perfusion to the diabetic or prediabetic heart, we may improve cardiac mechanics and, in so doing, prevent or slow the progression to clinical heart failure and possibly death. Although some of these pathophysiologic mechanisms have been explored in experimental animal models, the gaps between these experiments in animals and applications in humans are just beginning to be addressed.

Thus, we believe that the use of physiologic imaging techniques, integrated into the continuum of clinical care to understand the mechanisms linking inflammation to cardiovascular complications, is not only innovative, but will also facilitate needed clinical translation.

## II. SPECIFIC AIMS

Coronary flow reserve (CFR, calculated as the ratio of hyperemic over rest myocardial blood flow) is emerging as a powerful quantitative prognostic imaging marker of clinical cardiovascular risk. CFR provides a robust and reproducible clinical measure of the integrated hemodynamic effects of epicardial CAD, diffuse atherosclerosis, and microvascular dysfunction on myocardial tissue perfusion. Inflammation is a key mediator of this constellation of abnormalities, affecting the entire coronary vasculature, but no clinical trial to date has shown that directly reducing inflammation lowers cardiovascular event rates. As such, the recently launched Cardiovascular Inflammation Reduction Trial (CIRT) provides a unique opportunity for mechanistic investigation of the impact of anti-inflammatory therapy on changes in CFR as a reflection of coronary vascular dysfunction, which may precede clinical outcomes, particularly in patients at high-risk of events. We are ideally positioned to examine the impact of inflammation on CFR, having extensive experience in both the quantitation of CFR using clinically-integrated dynamic positron emission tomography (PET) and the ability to assess its association with cardiovascular outcomes.

The *central hypothesis* of this ancillary proposal, CIRT-CFR, is that reducing systemic inflammation using low-dose methotrexate (LDM) will, compared to placebo, quantitatively improve myocardial blood flow and coronary flow reserve as measured by PET over 1-12 months, in stable CAD patients with type 2 diabetes or metabolic syndrome enrolled in CIRT. In so doing, improvement in coronary vasoreactivity, endothelial function, and tissue perfusion may have beneficial effects on myocardial mechanics, left ventricular deformation and function and, ultimately, symptoms and prognosis.

**AIM 1.** To test the hypothesis that systemic inflammation is a critical determinant of coronary flow reserve and myocardial tissue perfusion, as assessed by quantitative PET imaging, in stable CAD patients with type 2 diabetes or metabolic syndrome. Specifically, we propose that treatment with LDM at a target dose of 15 to 20 mg orally weekly for 1-12 months will, compared to placebo, result in:

**Hypothesis #1:** Improved global coronary flow reserve in response to dipyridamole, reflecting primarily endothelium-independent vasodilation.

**Hypothesis #2:** Reduced total stress perfusion deficit, a semi-quantitative score that combines scar and ischemia.

**AIM 2.** To test the hypothesis that LDM at a target dose of 15 to 20 mg orally weekly for 1-12 months will, compared to placebo, result in improved left ventricular (LV) myocardial mechanics, as assessed by transthoracic echocardiography, and that this functional improvement will be correlated with the change in coronary flow reserve after 1-12 months of treatment. In this population of patients without severe heart failure, we propose to test the following hypotheses:

**Hypothesis #3:** LDM for 1-12 months will result in improved LV systolic function, as assessed by measures of LV peak global longitudinal strain, and diastolic function, as assessed by measures of tissue Doppler mitral annular early diastolic relaxation velocity (E').

**Hypothesis #4:** Changes in LV systolic and diastolic function after 1-12 months of LDM therapy will be correlated with changes in coronary flow reserve.

### III. SUBJECT SELECTION

Inclusion and exclusion criteria were selected to reflect those of the parent CIRT study. Specifically:

#### **Inclusion criteria:**

- a. Age  $\geq 18$  years at screening;
- b. Documented past history of MI OR past evidence of multivessel CAD by angiography, completed any planned coronary revascularization associated with a qualifying event at least 60 days prior to enrollment, and clinically stable for  $\geq 60$  days prior to enrollment; qualifying prior MI must be documented either by hospital records, evidence on current ECG of Q waves in 2 contiguous leads, and/or an imaging test demonstrating wall motion abnormality or scar; qualifying evidence of multivessel CAD by angiography must be documented by CAD in at least two major epicardial vessels defined either as the presence of a stent, a coronary artery bypass graft, or an angiographic lesion of 60% or greater (left main CAD that has been revascularized with a stent or bypass graft will qualify as multivessel disease, as will the presence of a 50% or greater isolated left main stenosis);
- c. History of type 2 DM or metabolic syndrome (meeting 2004 AHA/NHLBI definition\*) at time of study enrollment; \*includes any 3 of the following 5 diagnostic criteria: waist circumference  $\geq 102$  cm in men or 88 cm in women; triglycerides  $\geq 150$  mg/dl or on drug treatment for elevated triglycerides; high-density lipoprotein cholesterol (HDL-C)  $< 40$  mg/dL in men or  $< 50$  mg/dL in women or on drug treatment for reduced HDL-C; systolic blood pressure  $\geq 130$  mm Hg or diastolic blood pressure  $\geq 85$  mm Hg or on drug treatment for hypertension; and elevated fasting glucose  $\geq 100$  mg/dL or on drug treatment for elevated glucose.
- d. Willingness to participate as evidenced by signing the CIRT and CIRT-CFR informed consent.

**Exclusion criteria:**

- a. Prior history of chronic infectious disease, tuberculosis, or severe fungal disease; chronic hepatitis B or C infection; renal insufficiency; interstitial pneumonitis, bronchiectasis, or pulmonary fibrosis; known chronic pericardial effusion, pleural effusion, or ascites; chronic liver disease; myeloproliferative disorders in the past 5 years; non-basal cell malignancy or treated lymphoproliferative disease within the past 5 years; known HIV positive; life expectancy of <3 years;
- b. Chronic inflammatory condition such as lupus or rheumatoid arthritis, ulcerative colitis or Crohn's disease
- c. White blood cell count <3,500/ul, hematocrit < 32 percent, or platelet count < 75,000/ul
- d. Liver transaminase levels (AST or ALT) >upper limit of normal (ULN) or albumin < the lower limit of normal (LLN);
- e. Creatinine clearance < 40 ml/min as estimated with the Cockcroft-Gault equation;
- f. History of alcohol abuse or unwillingness to limit alcohol consumption to less than 4 drinks per week
- g. Women of child bearing potential, even if they are currently using contraception, and women intending to breastfeed.
- h. Men who plan to father children during the study period or who are unwilling to use effective forms of contraception.
- i. Requirement for use of drugs that alter folate metabolism (trimethoprim/sulfamethoxazol) or reduce tubular excretion (probenecid) or known allergies to antibiotics making avoidance of trimethoprim impossible;
- j. Current indication for methotrexate therapy;
- k. Chronic use of oral steroid therapy or other immunosuppressive or biologic response modifiers (see Exclusionary Medication List in Manual of Operations). Eligible study participants will be encouraged to have up to date pneumococcal and influenza vaccinations as recommended based on their age and underlying medical conditions.
- l. Chest X-ray evidence in the past 12 months of interstitial pneumonitis, bronchiectasis, or pulmonary fibrosis. For participants who do not have a chest X-ray in the prior 12 months, a chest X-ray will be obtained at baseline as part of the study protocol.
- m. New York Heart Association Class IV congestive heart failure.

[figure not shown]
**IV. SUBJECT ENROLLMENT**

We propose to recruit 150 patients for CIRT-CFR. This will be a collaborative effort between 6 clinical sites, with 4 sites in the Boston area: (1) *Brigham and Women's Hospital, BWH* (PI: [name]), (2) *Joslin Diabetes Center* (PI: [name]), (3) *Massachusetts General Hospital* (PIs: [name], and [name]), (4) *North Shore Medical Center* (PI: [name]), and two additional sites in the Ottawa area: (5) *Ottawa Heart Institute, OHI* (PI: [name]), and in Birmingham, Alabama: (6) *University of Alabama, UAB* (PI: [name]). We will have 3 imaging sites (BWH, PI: [name] [name]; OHI, PI: [name]; and UAB, PI: [name]), with **BWH serving as the Core Imaging Lab**, and all 4 Boston area sites referring patients for imaging to BWH. The subjects of the trial will be patients with CAD and type 2 DM or metabolic syndrome enrolled in the parent study (CIRT) and recruited from participating

CIRT sites local to BWH, OHI, and UAB. All patients identified at the 6 participating clinical sites as being potentially eligible for CIRT are automatically eligible for participation in this ancillary study.

## V. STUDY PROCEDURES

Randomization and double-blind study treatment period to either placebo or LDM (1:1) of willing and eligible patients will occur at the end of the open label run-in phase per the parent CIRT protocol, and will be stratified by time since the qualifying event ( $< 6$  or  $\geq 6$  months from the date of MI or most recent angiogram), type of event (MI or multivessel CAD), presence of either type 2 DM or metabolic syndrome, and site, which will ensure balance in the proposed study. Patients willing to participate in CIRT will be asked to enroll into the sub-study and may sign the CIRT-CFR informed consent at any point between signing the parent CIRT informed consent and completing the parent CIRT randomization visit (Visit 4). After giving informed consent for the ancillary CIRT-CFR, patients will undergo the baseline PET scan along with echocardiography at any point between the parent CIRT post run-in visit (Visit 3) and up to 4 weeks after randomization (Visit 4). Per the parent CIRT protocol: i) blood will be collected and stored for biomarkers at baseline (Visit 3), ii) patients will complete quality of life (SF-36) questionnaires at enrollment (Visit 2) and 1-12 months (Visit 7) after randomization, and iii) patients will be called at 3, 6, and 10 months after randomization to assure compliance. Final PET scan and echocardiogram will occur at approximately 1-12 months after randomization or within 4 weeks ( $\pm 2$  weeks) of Visit 7. At that time, blood will be collected and stored for biomarkers (using the same protocol as in the parent CIRT) to coincide with follow-up imaging in CIRT-CFR. The data collection schedule for CIRT and CIRT-CFR is summarized in the Appendix. Trial schema is as follows:

Imaging will be performed at the 3 imaging centers (BWH, OHI, and UAB). To minimize participant and site burden, only a baseline and single follow-up imaging time point will be pursued. The CIRT-CFR Screening Visit has been incorporated into the Consent Visit in an attempt to further reduce participant and site burden. Imaging tests (PET and echo) will be scheduled on the same day for patient convenience if possible, and no more than one week apart. “Baseline” study visit imaging will follow the open label run-in period of the parent trial to enhance long-term compliance and eliminate risk of radiation exposure for any individuals with immediate intolerance to the LDM study protocol. The imaging tests proposed are non-invasive, routinely performed, and historically well tolerated by patients. The radiation incurred through PET scanning is small ( $\sim 2.8$  mSv per study), and comparable to that incurred by an average American in a given year from background radiation. Clinical coordinators will be encouraged to enroll all CIRT-eligible patients at the 5 clinical sites participating in this ancillary study, so as to remove the possibility of selection bias. To minimize and understand potential selection bias, we will maintain an evaluation log of all patients who were screened and enrolled at the 6 sites.

**Timing of baseline imaging assessments.** Baseline PET scanning and echocardiography will follow CIRT's post run-in (open label, 6-8 week run-in phase) visit. The justification for this decision is based on the pharmacodynamics of LDM in rheumatoid arthritis, as well as additional biologic and trial logistic reasons. There are no data on the timing of changes in myocardial blood flow following LDM. Methotrexate is a prodrug that becomes active only when polyglutamated within cells, a slow iterative process that can take as long as ~27 weeks to reach steady state. In patients with rheumatoid arthritis, a clinical response to methotrexate usually begins within the first 6–12 weeks after initiation of therapy, with a maximal response observed at 6 months. This suggests that the longer-chain polyglutamates, which take longer to become detectable and reach steady state, have a more important role in the clinical response to methotrexate.

**Timing of follow-up imaging assessments.** Follow-up PET scanning and echocardiography will occur between 1 and 12 months post randomization.

**Positron Emission Tomography (PET):** Regional and global myocardial blood flow (MBF) will be assessed using PET imaging in accordance with the study-specific acquisition protocol. The investigative teams at BWH, OHI, and UAB have extensive experience in performing these procedures, and quantifying myocardial blood flow. PET scans will be performed using a whole body PET/CT scanner. Anti-hypertensives and beta-blockers will be withheld on the morning of the study. Patients will be allowed to continue using sublingual nitroglycerin as needed. Studies will be performed after 4 hours of fasting and 24 hours of abstinence from caffeine. The visit will take approximately 5 hours, including patient preparation. MBF will be measured at rest and during dipyridamole, adenosine, or regadenoson infusion, using N-ammonia or Rubidium, as the flow tracer. Importantly, the same radiopharmaceutical should always be used for the baseline and follow-up scans. After transmission imaging and beginning with the intravenous (IV) bolus administration of N-ammonia (~10-20 mCi, adjusted based on whether 2D- or 3D-imaging is used) or Rubidium (~10-20 mCi for 3D imaging), list mode images will be acquired for 20 or 7 minutes, respectively. Thirty (N-ammonia) or 10 (Rubidium) minutes later, patients will undergo a standard infusion of dipyridamole (0.56 mg/kg over 4 minutes), adenosine (0.14 mg/kg/min for 4 minutes), or regadenoson (0.4 mg bolus over 10 seconds). At peak hyperemia, a second dose of N-ammonia (~10-20 mCi, adjusted based on whether 2D- or 3D-imaging is used) or Rubidium (~10-20 mCi for 3D-, and 30-50 mCi for 2D imaging) will be injected IV, and images recorded in the same manner. The heart rate, blood pressure, and 12-lead ECG will be recorded at baseline and throughout the infusion of dipyridamole, and at recovery. All studies will be reviewed at the sites by site investigators for clinically important findings. All PET scans will be done for research (non-clinical) purposes only. For safety reasons, all studies will be reviewed at the sites by site investigators for clinically important findings. No reports or analyses will be provided to sites from the PET core laboratory and studies will not be assessed in real-time.

**Two-dimensional echocardiography:** Echocardiograms will be performed by site sonographers trained and certified by the echo core laboratory in the study-specific acquisition protocol. The noninvasive core laboratory at BWH has extensive experience in quantitative echocardiography in the context of therapeutic clinical trials. [name] also directs the core laboratory in the analysis of echocardiographic images in the NIH-funded ARIC study. Images will be acquired as recommended by the American Society of Echocardiography (ASE) and in a manner consistent

with standard practices for patient comfort and position. In addition, the echo protocol includes specific views to ensure optimal imaging for specific views to: (1) assess LV diastolic function, and (2) ensure optimal imaging for off-line LV deformation analysis with speckle-tracking software (i.e., images of the LV will be captured at high frame rates of 50-70 fps). The protocol will take approximately 35 minutes, including patient preparation. A superset of a standard echo exam will be performed, emphasizing endocardial border optimization and on-axis imaging. All studies will be acquired and stored in digital DICOM format, with CD/DVD copy for site backup. All studies will be reviewed at the sites by site investigators for clinically important findings. All echos will be done for research (non-clinical) purposes only. No reports or analyses will be provided to the sites from the echo core laboratory and studies will not be assessed in real-time.

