## VI. BIOSTATISTICAL ANALYSIS

CIRT-CFR sites participating in the proposed ancillary study. Based on our power analysis and sample size calculations, we estimate that each of the 6 clinical sites will be required to enroll approximately 25 patients over approximately 3 years. This is equivalent to 1 patient every 6 weeks per site, which we believe is reasonable and attainable. All sites have received IRB approval for the parent study and are actively enrolling patients in the parent CIRT trial. The proposed imaging studies (PET scans and echos) are routinely performed at the 3 imaging sites (BWH, OHI, and UAB). Drs. [name] (PI) and [name] (both at BWH), [name] (OHI), and [name] (UAB) are recognized experts in quantitative PET imaging and echocardiography, have published widely on these topics, and have extensive experience in conducting clinical trials using imaging endpoints.

***Aim 1. To test the hypothesis that systemic inflammation is a critical determinant of coronary flow reserve (CFR) and myocardial tissue perfusion, as assessed by quantitative PET imaging, in stable CAD patients with type 2 DM or metabolic syndrome.*** Specifically, we propose that treatment with LDM at a target dose of 15 to 20 mg orally weekly for 1-12 months will, compared to placebo, result in:

***Hypothesis #1:*** Improved global CFR in response to dipyridamole, reflecting primarily endothelium-independent vasodilation.

***Hypothesis #2:*** Reduced total stress perfusion deficit, a semi-quantitative score combining scar and ischemia.

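### Does allowing three stress agents undermine a primary endpoint worded for dipyridamole?

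*Combined protocol and SAP*

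**What the plan says.** Section II (Aim 1) states Hypothesis 1 as "Improved global coronary flow reserve in response to dipyridamole", and section VI (Aim 1) repeats it as "Improved global CFR in response to dipyridamole". The primary endpoint, the key secondary endpoint, the outcome variable of the primary model and the primary row of Table 1 are also tied to dipyridamole. The planning SD of 0.45 comes from earlier dipyridamole measurements.

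The PET paragraph of section V is wider: "MBF will be measured at rest and during dipyridamole, adenosine, or regadenoson infusion". Its one visible matching rule is that "the same radiopharmaceutical should always be used for the baseline and follow-up scans". The same paragraph says blood flow is assessed "in accordance with the study-specific acquisition protocol"; that acquisition protocol is not reproduced.

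Three other places bear on the point:

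- Section VII (Vasodilator Risks) presents dipyridamole as the study's stress agent. It lets an investigator choose adenosine or regadenoson for a patient with a contraindication.
- Section I defines CFR as the "ratio of global myocardial blood flow quantified at stress over that at rest" and section II as "calculated as the ratio of hyperemic over rest myocardial blood flow". Neither names an agent.
- Section VI (Aim 1, Statistical analyses) leaves out only patients without a repeat PET scan. The covariates are stratum, time since MI, imaging site, baseline CFR and treatment, with no term for the agent.

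**The concern.** Two things look wrong.

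The first is definition. Read literally, a patient stressed with adenosine or regadenoson has no value of the primary endpoint, yet the only stated exclusion would keep that patient in. If the two readings gave different analysis sets, there could be an argument after the data are in about which set is primary.

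The second is noise. The outcome is a within-patient change in a ratio whose numerator is stress flow. The authors saw that the tracer must match between scans, but the visible text says nothing similar about the agent that produces the stress flow. A patient who changed agent could show a change in CFR unrelated to treatment. The planning SD would not include that variance, so the stated power could be too high.

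**Working it through.** **Inputs from section VI, Aim 1, Power calculations and Table 1.** Difference δ = 0.24; SD of change σ = 0.45; two-sided α = 0.05; 130 evaluable patients, 65 per arm under the 1:1 allocation of section V.

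**The plan's own figure.** Two-sample t-test with noncentrality δ/σ × √(65/2) = 0.24/0.45 × 5.701 = 3.040 on 128 degrees of freedom (critical value 1.979). Power is 85.49%, against the stated 85%. The same method gives total N of 114, 130 and 150 for 80%, 85% and 90% power, exactly as in Table 1.

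**Which pairs matter.** A patient given the same agent twice, whichever it is, provides a comparable pair. Only a change of agent within a patient adds noise. Under section VII that needs a contraindication that appears or resolves between scans, or a swap between the two alternatives. The one concrete case named there, a history of seizures, would normally apply at both scans.

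**Effect of mismatched pairs (assumed inputs).** Let q be the share of pairs with a change of agent and d the CFR shift it causes. The documents give neither. If changes go equally in both directions, SD = √(0.45² + q·d²). If all go one way, SD = √(0.45² + q(1−q)·d²). For example, q = 0.10 and d = 0.20 in both directions gives √(0.2025 + 0.0040) = 0.4544.

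| q | d | Power, both directions | Power, one way | Loss (points) |
|---|---|---|---|---|
| 0 | – | 85.49% | 85.49% | 0 |
| 5% | 0.20 | 85.15% | 85.17% | 0.3 |
| 10% | 0.20 | 84.81% | 84.88% | 0.6–0.7 |
| 10% | 0.24 | 84.51% | 84.61% | 0.9–1.0 |
| 20% | 0.20 | 84.13% | 84.40% | 1.1–1.4 |
| 20% | 0.24 | 83.53% | 83.92% | 1.6–2.0 |

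A shift of 0.24 equals the whole planned treatment effect. At d = 0.20, unadjusted power stays at 85.0% or more until about 7% to 8% of pairs are mismatched.

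**Offset from baseline adjustment.** The planned model includes baseline CFR, which the power calculation ignores. With equal variances at the two scans and between-scan correlation ρ, the squared correlation between baseline and change is (1−ρ)/2. Adjustment fully offsets the added variance when (1−ρ)/2 ≥ q·d²/0.45². For q = 10% and d = 0.20 the right side is 0.0040/0.2025 = 0.0198, so any ρ up to 0.96 is enough. For q = 20% and d = 0.24 it is 0.01152/0.2025 = 0.0569, so ρ up to 0.886. The documents give no ρ. Simulated adjusted power at ρ = 0.9 is 86.7–87.1% with no mismatch and 86.2–86.3% at q = 10%, d = 0.20.

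**Bias.** If changes of agent are equally frequent in both arms, the treatment difference is not shifted. If they differed, the bias would be the difference in shares times d. A 5-point excess in one arm with d = 0.20 gives 0.05 × 0.20 = 0.01, about 4% of 0.24.

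**The case for a change.** The strongest opposing case concerns the definition, not the power. The named endpoint and the stated exclusion rule do not fit together for patients given an alternative agent. If the literal wording were followed and an assumed 5% or 10% of the 130 fell outside it, power would be 83.6% or 81.6%. Section V does not repeat the contraindication limit of section VII, and no visible passage says the agent is recorded. Aligning the wording and adding one field would be nearly free.

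Much of this is true as a description. The wording is narrower than the imaging procedure, and the analysis set is not settled beyond argument, because the Statistical analyses paragraph that sets the exclusion also ties the outcome to dipyridamole. A larger disturbance than those tabulated is also conceivable: 20% of pairs with an added SD of 0.45 would bring power to about 79%.

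What does not stand is that the plan must change:

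- A general definition of CFR and a label naming the usual agent do not conflict. Section VII qualifies the list in section V and does not contradict it.
- Faced with a patient who has two valid scans, an analyst following the only stated exclusion and the general definition of CFR would include that patient. This also keeps the randomised groups together.
- A rule to keep the same agent where the clinical choice allows would be suspended in most cases where a change occurs, because a new contraindication is the main reason for one.
- Recording or matching may already be covered in the acquisition protocol or the data collection schedule, neither of which is reproduced. The visible text cannot establish a gap.
- A supportive analysis of same-agent pairs would select on a choice made after randomisation. If mismatches are rare it would nearly repeat the primary result.

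**Conclusion.** The concern does not call for a change. The endpoint label names the default agent, and the imaging section lists what may be used when that agent is contraindicated; analysts can bridge the two sensibly. Followed as written, the plan still gives a sound blinded, randomised comparison.

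The stated 85% power reproduces and is not shown to be wrong. The illustrative loss is under one point for up to 10% mismatched pairs and about 1.1 to 2.0 points at 20%, for shifts of 0.20 to 0.24, before any gain from baseline adjustment. These sizes rest on assumed shares and shifts and are not upper bounds. The conclusion rests on three readings: the contraindication limit in section VII governs the list in section V; changes of agent are therefore uncommon; and blinding leaves no reason to expect them to differ materially by arm. Which agent a patient receives is a clinical matter and is not at issue here.
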